Patients will be randomized by pharmacy into 2 groups, a control group and a treatment group. The treatment group will be provided with a 6 month supply of probiotic supplementation; the control group will be given a placebo for 6 months along with instructions on how to take the supplement. Subjects will receive a 1 month (+/- 1 week) phone call follow up to ensure adherence to study instructions and daily oral intake of supplement and again at 3 months (+/- 1 week).

Study participation will end at 6 months (+/- 2 weeks) after the repeat of liver enzymes, hemoglobin A1C, lipid panel, assessment of BMI and transient elastography as completed at scheduled clinical appointment.

TABLE OF EVENTS

	Pretreatment	1 month +/-1 week	3 month +/-1 week	6 month +/-2 weeks
Consent	Х			
Capsules dispensed	Х			
Diet & exercise plan explained	Х	Х	Х	
Labs drawn	Х			Х
Liver scan done	Х			Х
Phone call		Х	Х	
Remaining capsules returned				Х

RISKS AND BENEFITS

The FDA has identified the study as minimal risk and exempt of the need for an IND number.

There are currently no alternative treatments or procedures indicated in this disease process, hence, the purpose of the study. However, potential benefits to subjects from exercise (walking) intervention and nutritional coaching may improve the elasticity and function of the liver.

Potential risks include GI symptoms related to probiotic use such as gas and bloating. The recommended exercise is walking.

VI. ELIGIBILITY CRITERIA

Inclusion Criteria:

- Diagnosis of NAFLD and/or NASH
- Subject aged 18 and older
- Non-pregnant Self-reported
- Subject with decision making capacity to understand and consent to study procedures
- Ability to follow study related activities regarding medications, diet and exercise

Exclusion Criteria:

• Without diagnosis of NAFLD or NASH

- History of liver disease from other causes, including but not limited to hepatitis, autoimmune, alcohol use, fatty liver of pregnancy, Wilson's disease, primary or secondary hemochromatosis
- Patients aged less than 18 years
- Self-reported pregnant patients
- Inability to understand, follow and consent to study procedures
- Received a liver scan greater than 2 months prior to enrollment
- Patient lost more than 5 pounds of weight in the last 2 months
- Hepatic decompensation defined as gastrointestinal bleeding, ascites, hepatic encephalopathy
- Inability to engage in exercise
- Currently immunocompromised or taking immunosuppressive drugs

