Categorical data will be summarized as counts and percentages, and continuous data as means with corresponding standard deviations. Pre- post- results will use the chi-square test for association for nonparametric data or analysis of covariance for parametric data. Because multiple measures will be obtained for achieving the secondary objectives, multivariate analyses will be used for exploring overall treatment effects. Throughout this study, a p-value<0.05 (two-tail) will be considered statistically significant.

DATA AND SAFETY MONITORING PLAN

The Principal Investigator and the co-investigators will do safety monitoring. Ongoing assessment of subject safety will be monitored during subject phone calls as detailed in methodology. Any reported problems will be discussed with Medical Monitor/ Principle Investigator. Subjects with any signs or symptoms of hepatic decompensation or elevated liver enzymes beyond three times the upper limit of normal will be removed from the study, the study will be aborted for that subject and immediate diagnostic and/or therapeutic modalities will be delivered. It should be noted that our study is defined as minimal risk as also identified by the FDA with the exemption of need for an IND number.

Any subject found to be noncompliant with the protocol will be removed from the study and asked to return their medications to the office. The medications will then be returned to the research pharmacist.

All data will be kept electronically in a secure SharePoint site. Hard copies will be kept in a locked file located in a locked office until the study ends. Hard copies will then be scanned into the SharePoint site and shredded per Beaumont policy.

REFERENCES

[1] The Liver Meeting, Post-Graduate Seminar, New Research, American Association for the Study of Liver Diseases, Washington, D.C., 2017

Velasco, Nicolas; Contreras, Alvaro; Grassi, Bruno. The Mediterranean diet, hepatic steatosis and nonalcoholic fatty liver disease. Current Opinion in Clinical Nutrition & Metabolic Care. 17(5):453-457, September 2014.

Attachments

- A. PRONE Study Informed Consent Form and Authorization for Disclosure of Protected Health Information
- B. PRONE Study FDA 2018-1186 Signed Final Response
- C. PRONE Study Nutrition Program

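### No symptom enquiry is specified after the month-3 call, which leaves about half of the six-month exposure to spontaneous reporting

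*Combined protocol and SAP*

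**What the plan says.** The Data and Safety Monitoring Plan names one means of ongoing safety assessment and refers elsewhere for its detail: "Ongoing assessment of subject safety will be monitored during subject phone calls as detailed in methodology". The same section says that problems which are reported go to the medical monitor or principal investigator. It removes a subject who shows clinical evidence of hepatic decompensation or whose liver enzymes exceed 3 times the upper limit of normal.

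The Methods section describes the calls as follows: "Subjects will receive a 1 month (+/- 1 week) phone call follow up to ensure adherence to study instructions and daily oral intake of supplement". The call is repeated at 3 months, again with a window of 1 week either side, and no later call is listed. On exposure, Methods says: "The treatment group will be provided with a 6 month supply of probiotic supplementation"; the control group receives placebo for the same period. On the last contact: "Study participation will end at 6 months (+/- 2 weeks) after the repeat of liver enzymes, hemoglobin A1C, lipid panel, assessment of BMI and transient elastography".

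In the Table of Events, the two call columns show the call itself and the diet and exercise explanation. The month-6 column shows labs, liver scan and return of capsules. No row concerns symptoms or adverse events, and labs are drawn only before treatment and at month 6. The Risks and Benefits section identifies the expected product harms: "Potential risks include GI symptoms related to probiotic use such as gas and bloating".

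**The concern.** The safety plan relies on content that it says is set out in the methodology, and that content is not there. The calls also end halfway through treatment. Gas and bloating, the product risks given as examples, do not appear on a blood test or a liver scan; they are found by asking or by the subject volunteering them. The decompensation trigger likewise depends partly on symptoms.

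With no specified question after month 3, the record of later harms depends on who chooses to speak up. There is also no stated question set, so what is asked at the two calls may vary between subjects and between callers. The monitoring plan separately removes subjects who do not comply. Someone who stops the capsules because of bloating could be recorded as noncompliant, since no question about the reason is planned. The trial's goal is to support probiotics as a possible treatment, and a reader of its results will want to know how the product was tolerated over the whole six months.

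**Working it through.** The plan states no figure on this point, so there is none to reproduce. The check sets the sections side by side and then measures the time after the last call.

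**Scheduled contacts and what each specifies**

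| Contact | Listed content (Methods, Table of Events) | Safety role elsewhere | Symptom questions specified |
|---|---|---|---|
| Month 1 call | Adherence, diet and exercise | Yes, by the Data and Safety Monitoring Plan | None given |
| Month 3 call | Adherence, diet and exercise | Yes, by the Data and Safety Monitoring Plan | None given |
| Month 6 visit | Enzymes, HbA1c, lipids, BMI, elastography, capsule return | AST/ALT bear on the enzyme removal rule | None given |

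The Data Collection section lists only the scan, the laboratory tests and BMI. The endpoints under Objectives include no harms measure, and the Statistical Methodology section describes no adverse-event table. The omission is consistent across the document, so it is unlikely to be a table row lost when the file was read.

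**Share of exposure after the last call**

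Inputs: last call at month 3, taken as week 13 ± 1 (weeks 12 to 14); final visit at month 6, taken as week 26 ± 2 (weeks 24 to 28). Both windows come from Methods and the Table of Events.

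Formula: share = (final visit − last call) / final visit.

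- Nominal: (26 − 13) / 26 = 13/26 = 50%.
- Smallest (late call, early visit): (24 − 14) / 24 = 10/24 = 42%.
- Largest (early call, late visit): (28 − 12) / 28 = 16/28 = 57%.

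The same calculation in days, with a month of 365.25/12 = 30.44 days, gives 91.3/182.6 = 50.0%, 70.3/168.6 = 41.7% and 112.3/196.6 = 57.1%.

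These shares treat exposure as running to the final visit. If the capsules instead stop at week 26 and the visit falls later, the largest share is (26 − 12) / 26 = 14/26 = 54%. About half is right on either basis.

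**The case against.** The strongest reply is that the two sections complement each other. Methods gives adherence as a purpose of the calls but does not say it is the only one, and the Data and Safety Monitoring Plan adds safety in plain words. Its reference to the methodology can be read as pointing to when the calls happen, which Methods does state. That reply stands for months 1 and 3. A reader might infer that the calls are for adherence alone, so that nobody is ever asked about harm and planned safety coverage is zero. The documents do not support this, because a site follows the whole protocol, including the monitoring plan. What is missing at those two contacts is the content of the enquiry.

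The reply also notes that month 6 is a clinic visit with repeat liver enzymes. This is correct, and it is wrong to say that the visit yields no safety information. The enzymes are not a symptom enquiry, however, and they arrive at the end of exposure.

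Third, subjects may report problems unprompted, the monitoring plan provides for that, and the consent form (Attachment A, not available here) may tell them how. This limits the concern but does not answer it: spontaneous reports are not planned collection, and the monitoring plan relies on the methodology, not on the consent form.

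Finally, the product is sold over the counter, the study is described as minimal risk, and no safety endpoint or comparison of harms between arms is planned. That context argues for a light remedy. It also means the gap does not undermine any inference that the plan itself proposes to make.

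**Conclusion.** The point holds as a gap in harms ascertainment. The contact schedule, followed exactly, specifies no symptom enquiry for harms that begin after the month-3 call. That period is nominally 50% of exposure, with a range of 42% to 57% across the permitted windows. The figure rests on the stated schedule and on exposure continuing to the final visit. It assumes that the calls at months 1 and 3 do serve as safety contacts, as the monitoring plan says.

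A reader might go further and infer that about half of all adverse events would be missed. The documents do not support that. It would require onset to be spread evenly over the six months, and they give no onset data; if symptoms cluster early, the share is smaller. The percentage describes time without a specified enquiry. It does not count lost events, and a question at month 6 with adequate recall could recover much of what happened in that time.

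One related inconsistency remains. The removal rule depends on symptoms and on enzyme values, yet after month 3 no contact is scheduled until participation ends, and no enzymes are scheduled between baseline and month 6. The Data and Safety Monitoring Plan and the schedule in Methods must be reconciled on this.

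**What to change.** Add one row to the Table of Events for adverse events and symptoms (gastrointestinal symptoms and symptoms of decompensation), marked at the 1-month call, the 3-month call and the 6-month visit. Use the same short question set in both arms, asked while blinded, with recall back to the previous contact. Amend the description of the calls in Methods so that their stated purpose includes safety and matches the Data and Safety Monitoring Plan. Add a line to Statistical Methodology that events will be tabulated by arm.

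The cost is protocol wording, one case-report page and a few minutes at each of three contacts that already exist; no visit or procedure is added. More minor gastrointestinal complaints will be recorded.

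This change completes the record of harms but does not provide timely detection between months 3 and 6, because it adds no contact in that interval. How the removal rule is to operate during that time, given the contact schedule, is for the sponsor to reconcile.

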Our hypothesis is that introducing a benign probiotic (beneficial intestinal bacteria) using Align probiotics will cause improvement in hepatocellular (liver tissue) injury and fibrosis. Align is a once daily over-the-counter defined by the Food and Drug Administration as a new dietary ingredient. Each Align capsule contains one billion beneficial live bacteria/CFU, known as Bifidobacterium 35624. Our goal is to provide data that probiotics may be a viable treatment option in the future for clinicians for NAFLD and NASH and to establish a link that the intestinal microbiome plays a role in liver inflammation.

IRB NUMBER: 2019-129
IRB APPROVAL DATE: 04/07/2021

Primary Endpoint:

To determine if probiotic use improves fibrosis stage on transient elastography

Secondary Endpoints:

To determine if probiotic use improves:

- 1) Liver Enzymes (AST and ALT)
- 2) Hemoglobin A1C (Diabetic Marker)
- 3) BMI (Body Mass Index)
- 4) Lipids (LDL)

METHODS

NAFLD and NASH patients seen in office consultation at South Oakland Gastroenterology Associates in Farmington Hills, Michigan from 2019-2021 who have confirmed diagnosis of NAFLD or NASH and fit the eligibility requirements will be approached to participate in the double-blind, placebocontrolled study.

After preparation and randomization by the Beaumont research pharmacy, the probiotic and placebo capsules will be delivered to the office in groups of 10 bottles at a time. Capsule bottles will be numbered consecutively and pharmacy will keep the randomization log; patients and researchers will be blinded. The bottles will be stored in a locked cabinet in the clinic. Only pharmacy will hold the randomization key. A log will be used to track the receipt and distribution of the capsules.

After informed consent is obtained, subjects will be counseled on diet and exercise and a baseline transient elastography exam will be ordered and baseline liver enzymes (AST and ALT) will be drawn, including hemoglobin A1C, lipids in the form of LDL and assessment of BMI (all standard of care tests). The patients will receive information on a standardized Mediterranean diet based nutrition program as well as direction for recommended 30 minutes of aerobic exercise 3 times weekly. Our recommended nutrition program limits excessive alcohol to avoid a confounding variable.

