- Milk protein allergy
- Recent or active chemotherapy for malignancy
- Gastrointestinal malignancy
- Gastrointestinal disease such as Ulcerative Colitis, Crohn's Disease as these alter the microbiome
- Recent antibiotic therapy (within 6 months)
- Known allergy to probiotics
- History of major gastrointestinal surgery such as resection of the colon
- No concomitant use of probiotic from any source (i.e., kefir, certain yogurts, live culture sauerkraut)
- Any implanted battery operated device (i.e. AICD, pacemaker, loop recorder, cochlear implant)

DATA COLLECTION

Any changes to the liver will be documented using a non-invasive scan called transient elastography. Elastography is a technique similar to ultrasound that measures the stiffness and density of the liver and is a safer alternative to a liver biopsy. This is a standard of care procedure will be done at 0 months and 6 months. Along with the scans, the results of liver enzymes, standard of care laboratory tests used to follow the disease progression for patients with NAFLD and NASH, will be reviewed. These labs include AST and ALT, Hemoglobin A1C, BMI (Body Mass Index) and Lipids (LDL), also standard of care.

DATA ANALYSIS

A. Sample Size Consideration

Using paired measurements, a two-tail alpha of 0.05, a power level of 0.8, and assuming a large effect size (contingency coefficient of 0.447), it is estimated that 40 subjects (20 per group) would detect statistically significant between-group changes in liver function. Related studies on hepatic function (Wong, et al., 2013 and Aller, et al. 2011) following administration of probiotics over 6 and 3 months 03.30.2021

IRB APPROVAL DATE: 04/07/2021

duration demonstrated statistically significant changes with estimated large effect sizes using 20 and 28 subjects, respectively. A sample size of approximately 40 is expected to hold statistical significance, however, to account for dropouts or potential removal of subjects from study, a goal of 80 subjects are expected to be enrolled to ensure adequate sample size.

B. Statistical Methodology

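### The 3x ULN enzyme rule ends study participation rather than only study product, so a subject removed on an unscheduled draw loses the primary-endpoint scan for a reason tied to an outcome; few are likely to be affected

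*Combined protocol and SAP*

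**What the plan says.** The Data and Safety Monitoring Plan states that subjects with signs of hepatic decompensation or "elevated liver enzymes beyond three times the upper limit of normal will be removed from the study", that "the study will be aborted for that subject", and that diagnostic or therapeutic care follows at once. The next paragraph removes noncompliant subjects from the study as well.

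Under Objectives, AST and ALT are the first secondary endpoint, and fibrosis stage on transient elastography is the primary endpoint. Data Collection says that the scan "will be done at 0 months and 6 months". The Table of Events puts labs at pretreatment and month 6 only; the 1- and 3-month contacts are phone calls. Methods adds: "Study participation will end at 6 months (+/- 2 weeks) after the repeat of liver enzymes", together with the other labs and the scan.

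The plan deals with removed subjects in one place, Sample Size Consideration: "to account for dropouts or potential removal of subjects from study, a goal of 80 subjects are expected to be enrolled". Statistical Methodology names chi-square, analysis of covariance and multivariate analyses. It gives no analysis set and no method for missing values.

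**The concern.** The measurement that ends a subject's participation is itself an outcome, and the plan treats stopping treatment and leaving the study as one event. Nothing requires a removed subject to return at month 6. Because there is only one follow-up scan, a subject who leaves before then contributes nothing after baseline to the primary endpoint. Such losses would fall selectively on subjects with high enzymes. Enrolling extra subjects protects the sample size but does not correct a selective loss.

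With no scheduled labs between baseline and month 6, an early removal needs an enzyme value from outside the study schedule. Data Collection describes the enzymes as "standard of care laboratory tests used to follow the disease progression for patients with NAFLD and NASH", so clinical draws in between are plausible, but the documents give no frequency. The question is how many scans could be lost, and whether the AST/ALT comparison would be biased.

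**Working it through.** **The plan's own figure.** A contingency coefficient of 0.447 gives w = 0.447 / sqrt(1 - 0.447^2) = 0.4997. With a noncentral chi-square test at alpha 0.05, 80% power needs N = 32 at 1 degree of freedom, 39 at 2, and 44 at 3. The plan does not state the degrees of freedom; its 40 agrees with 2. Enrolling 80 to keep 40 allows a loss of 1 - 40/80 = 50%. This figure is not in dispute.

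**Assumed inputs.** The documents contain no enzyme data, so all of these are assumptions: log-normal ALT, median 1 to 2 x ULN, log SD (s) 0.5 to 0.7, correlation 0.6 between baseline, mid-study and month-6 values, and a true log effect of 0, -0.30 (benefit) or +0.30 (harm). A fraction p of subjects has one unscheduled draw, independent of the enzyme level.

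**Scans lost through unscheduled draws, no true effect.**
- P(above 3x ULN) = 1 - Phi[(ln 3 - ln median) / s].
- Scans lost per 80 = 80 x p x P.
- Low end: median 1.0, s = 0.5 gives 1.099 / 0.5 = 2.20, P = 1.4%, and 80 x 0.1 x 0.014 = 0.1.
- High end: median 2.0, s = 0.7 gives (1.099 - 0.693) / 0.7 = 0.58, P = 28.1%, and 80 x 0.2 x 0.281 = 4.5.

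The last two columns of the table belong to the separate reading described below it.

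| Median (x ULN) | s | P above 3x ULN | Scans lost per 80 at p = 10% / 20% / 50% | If month-6 values are excluded: benefit shrinks | Harm shrinks |
|---|---|---|---|---|---|
| 1.0 | 0.5 | 1.4% | 0.1 / 0.2 / 0.6 | 3.3% | 9.1% |
| 1.0 | 0.7 | 5.8% | 0.5 / 0.9 / 2.3 | 11.0% | 19.0% |
| 1.5 | 0.5 | 8.3% | 0.7 / 1.3 / 3.3 | 12.6% | 25.2% |
| 1.5 | 0.7 | 16.1% | 1.3 / 2.6 / 6.4 | 22.3% | 32.9% |
| 2.0 | 0.5 | 20.9% | 1.7 / 3.3 / 8.4 | 24.5% | 39.5% |
| 2.0 | 0.7 | 28.1% | 2.2 / 4.5 / 11.2 | 32.6% | 43.5% |

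The rule carries no time limit, so it may also remove subjects who are above 3x ULN at baseline. Among those who remain, the largest share above the limit later is about 17% instead of 28%, and the maximum at p = 20% becomes 80 x 0.2 x 0.17 = 2.7 scans.

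**AST/ALT bias from unscheduled draws** (simulation, 2,000,000 per arm, analysis of covariance on baseline, log scale).
- No effect, equal draw rates: within 0.0003 of zero.
- No effect, 20% probiotic and 10% placebo: -0.0004 to -0.0064. With the rates reversed: +0.0004 to +0.0061.
- No effect, 30% probiotic and 10% placebo: -0.0009 to -0.0132.
- True effect -0.30, equal rates of 10% to 20%: the estimate shrinks by 0.1% to 1.2%.

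No bias was computed for the primary endpoint. The documents give nothing that links enzyme level to change in fibrosis stage.

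**A reading that the plan does not state: month-6 values above 3x ULN are also excluded from analysis.** Shrinkage = 1 - (estimate without those values / estimate with all values). On the log scale a benefit shrinks by 3% to 33% and a harm by 9% to 44%. With no effect the estimate stays within 0.001 of zero. With baseline also limited to 3x ULN, the maxima are about 27% and 40%. Across correlations 0.4 to 0.8 the ranges are 2% to 39% and 5% to 50%. The plan names no log transform; on the raw scale at correlation 0.6 they are 8% to 63% and 20% to 74%.

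**The case against.** The best defence is the schedule. No study procedure yields an enzyme value between baseline and month 6, so the rule has little to act on. The draw rates are guesses, and the standard-of-care wording does not show that interim draws happen. A plan that can lose half its subjects will not run short of numbers because of 4 or 5 scans. The 3x ULN action is a reasonable safety measure. The broader gap is that no analysis population or missing-data method is defined, and that covers every kind of removal, noncompliance included.

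Most of this stands, and it limits the size of the point. It does not remove it: the text ends participation, and nothing brings those subjects back for the one follow-up scan.

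Three stronger readings are tempting, and the documents do not support them.
- A reader might infer that the highest month-6 AST/ALT values will be deleted. The plan does not say so. Those labs belong to the visit that ends participation, so the values are already recorded. The large shrinkage figures belong to this reading only.
- A reader might infer that draws differ by arm, because Risks and Benefits says "Potential risks include GI symptoms related to probiotic use such as gas and bloating". That is conjecture, and even 20% against 10% moves AST/ALT by no more than about 0.006 log units.
- A reader might take enzyme removals off the 40 subjects in the power statement. That counts them twice, because the 40 is already what is left after removals.

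**Conclusion.** The point holds in a limited form. The rule as written ends data collection on the value of an outcome, and no analysis set or follow-up requirement keeps removed subjects in. The practical cost is a small number of lost primary-endpoint scans: about 0.1 to 4.5 of 80 at draw rates of 10% to 20%, with a maximum near 2.7 if the rule also acts at baseline, and up to about 11 if half of subjects had a draw. Bias in AST/ALT is negligible at the lower draw rates. Any substantial understatement of a benefit or a harm depends on an exclusion that the plan does not state, and even then there is no bias when there is no effect. The wording of the rule and the lack of any retention provision are certain. All the sizes rest on the assumed distributions and draw rates. This is a worthwhile low-cost improvement, not a threat to the trial's main conclusion.

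**What to change.** Separate stopping product from leaving the study. Suggested wording:

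> Subjects with AST or ALT above 3x ULN stop study product and receive clinical care. They remain in follow-up for the 6-month labs and scan where possible. All recorded values, including the triggering value, are kept, and all randomised subjects are analysed in their assigned group. The same applies to subjects who stop product for noncompliance.

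Report the number above 3x ULN by arm as a safety outcome. The threshold and the clinical action stay with the investigators. If the rule is meant to cover baseline values, check that result before a bottle is assigned. If it is not, do not add an enzyme eligibility limit: on the assumed inputs it would exclude 1.4% to 28.1% of subjects, or about 1 to 22 of 80.

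The cost is a wording change in the protocol and SAP, since the month-6 labs and scan are already planned for everyone. The downside is a month-6 visit for subjects stopped early, whose values may partly reflect the clinical care they received. If baseline values are covered, there is also a short wait before a bottle is assigned.

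### Noncompliant subjects are removed after randomisation and no analysis set is named, so by default the 6-month comparison covers subjects selected on compliance

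*Combined protocol and SAP*

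**What the plan says.** All references are to the combined protocol and SAP.

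- **Removal rule** (Data and Safety Monitoring Plan): "Any subject found to be noncompliant with the protocol will be removed from the study". No threshold is given. The inclusion criteria describe what subjects must be able to do: "Ability to follow study related activities regarding medications, diet and exercise". The rule could therefore reach capsules, diet or exercise.
- **When compliance is checked** (Methods): a "phone call follow up to ensure adherence to study instructions and daily oral intake of supplement" at 1 month, repeated at 3 months.
- **When outcomes are measured** (Methods, Table of Events): "Study participation will end at 6 months (+/- 2 weeks) after the repeat of liver enzymes" and the other assessments. On the scan, Data Collection says "This is a standard of care procedure will be done at 0 months and 6 months". No other post-baseline scan or blood draw is scheduled.
- **Sample size** (Data Analysis, A): about 40 subjects are needed, and "to account for dropouts or potential removal of subjects from study, a goal of 80 subjects are expected to be enrolled".
- **Analysis** (Data Analysis, B): chi-square or analysis of covariance on pre-post results, and multivariate analyses for the secondary outcomes. No analysis set is named. Nothing is said about analysis by assigned arm or about missing 6-month values.
- **Safety removal** (Data and Safety Monitoring Plan): for hepatic decompensation or an enzyme rise past a stated limit, "the study will be aborted for that subject".

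**The concern.** Removal can happen at month 1 or month 3, and the primary outcome is first measured after baseline at month 6. A pre-post test needs that second value. The sample-size text treats removal as a loss from the 80 enrolled. Together these mean that the comparison, by default, is among subjects who stayed compliant, and compliance is observed after randomisation.

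Such a comparison is biased if removal differs by arm and the extra removals in one arm are related to prognosis. Each ingredient is plausible. Risks and Benefits says "Potential risks include GI symptoms related to probiotic use such as gas and bloating", which could make noncompliance more frequent on probiotic. The same section suggests that exercise and nutritional coaching may help the liver, which could make compliance prognostic. The documents present these as separate mechanisms and do not show that the same removals carry both features.

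The second issue does not depend on removal rates. With no set named in advance, whom to count can be decided after results are seen. This includes subjects found noncompliant only at the 6-month visit, whose outcomes will exist.

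**Working it through.** **The plan's own figures.** From the contingency coefficient of 0.447, w = 0.447/√(1 − 0.447²) = 0.4997. With a two-sided alpha of 0.05 and 80% power, the noncentral chi-square gives N = 39 at 2 df. Using 0.447 directly as w gives N = 40 at 1 df. The stated 40 is reproduced on either reading. Enrolling 80 to keep 40 allows for a loss of 1 − 40/80 = 50%.

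**Bias, continuous outcome.** The removal rates and correlations are assumptions. Let adherence and outcome be standard normal with correlation r, with no true effect and 40 randomised per arm. If the lowest fraction p on adherence is removed, the mean outcome among those kept is r·φ(z_p)/(1 − p). The bias is the difference between arms. Type I error is from a two-sided z-test with SD 1 and 40(1 − p) kept per arm.

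For 20% v 40%, φ(z_p)/(1 − p) is 0.350 and 0.644. The bias is r × 0.294, which is 0.029 SD at r = 0.1 and 0.147 SD at r = 0.5.

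| Removed, placebo v probiotic | Bias (SD), r = 0.1 to 0.5 | Type I error |
|---|---|---|
| equal (20% v 20%, 50% v 50%) | 0 | 5.0% |
| 20% v 25-30% | 0.01 to 0.07 | 5.0% to 5.9% |
| 20% v 40% | 0.03 to 0.15 | 5.1% to 8.5% |
| 45% v 55% | 0.02 to 0.08 | 5.0% to 5.7% |

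The sign reverses if placebo loses more. A t-test simulation of 20% v 40% (20,000 runs) gave 5.3% to 8.8%. If 20% of each arm is removed for prognostic reasons and the extra probiotic removals up to 40% are random, simulated bias is 0.00 SD.

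**Bias, improved or not improved.** Under the same model, with 20% to 40% assumed to improve and a pooled two-proportion test, 20% v 25-30% gives 0.2 to 3.1 percentage points and 5.0% to 5.7% error. For 20% v 40% the figures are 0.8 to 6.3 points and 5.1% to 7.5%.

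A stronger assumption gives more. Suppose 60% would comply on either arm, 20% on placebo only and 20% on neither. Improvement is 40% in the first group and 10% in the others. Placebo subjects kept then improve at (0.6 × 0.40 + 0.2 × 0.10)/0.8 = 32.5%, against 40% on probiotic, a bias of 7.5 points. With 50% in the first group it is 50% − 40% = 10 points. Rejection is 8.9% to 12.0%, against 4.8% to 5.0% when all randomised subjects are analysed. Equal 40% removal gives 5.5% to 6.0% with no bias, so part of that excess comes from the test at small numbers.

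**ANCOVA** (simulation, 20,000 runs; assumed baseline correlation 0.7; 20% v 40%; r = 0.3 and 0.5).

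| Adherence is linked to | Bias (SD) | Type I error |
|---|---|---|
| baseline only | 0.00, 0.00 | 5.3%, 5.1% |
| baseline and later change | 0.04, 0.08 | 5.7%, 7.1% |
| later change only | 0.09, 0.15 | 7.6%, 13.5% |

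Adjustment removes the bias only if the link runs through baseline. In the last row the bias is unchanged while the residual SD falls to about √(1 − 0.7²) = 0.71, so the error rate rises.

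**Power if all 80 are analysed.** Using the plan's effect size and assuming noncompliers gain nothing, w becomes 0.4997c for a compliant fraction c. Power at 1 df / 2 df is 94.7% / 90.3% at c = 0.8, 87.9% / 80.7% at 0.7, 76.5% / 66.8% at 0.6 and 60.8% / 50.3% at 0.5.

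On a continuous scale, an assumed 0.9 SD effect (not in the documents) gives 81.2% at 20 per arm, close to the plan's target. With all 40 per arm, and 20%, 40% or 50% of the probiotic arm gaining nothing, the effect is 0.72, 0.54 or 0.45 SD and power is 89.6%, 67.5% or 52.1%. Compliers-only power is 95.0% at 32 v 32 and 91.5% at 32 v 24.

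**The case against.** The strongest reply is that exclusion is inferred. The removal sentence governs participation and the return of capsules, and nothing says that removed subjects' data are discarded. The 6-month scan and labs are standard of care, so values may exist for some of them. That is correct, and it is why the point is put as a default. It does not close the gap, because the plan does not commit to obtaining or using those values and it counts removal as a loss.

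Blinding also helps. Patients and researchers are blinded and only pharmacy holds the key, so staff cannot judge compliance by known arm. Blinding does not prevent noncompliance caused by the assigned capsule, nor choices made after unblinding.

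The 50% allowance covers dropouts and removals together. It is a planning margin, not an expected removal rate. Every bias figure rests on assumed rates and correlations, and many scenarios stay close to 5%. This stands: confidence is high about the omission, not about its practical effect.

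Finally, dilution is a real cost of analysing everyone. At 50% noncompliance, power is about 50% to 61%, well below the 80% planned. That trade-off should be settled in advance; it is no reason to leave the set unstated.

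**Conclusion.** The concern holds and should be fixed. It is certain from the text that noncompliant subjects are removed before the only outcome visit and that no analysis set or missing-outcome rule is stated. The bias is conditional. It is about zero if removal is equal by arm, or if the extra removals are unrelated to prognosis. In the main model, 20% v 40% removal gives 0.03 to 0.15 SD and 5.1% to 8.5% type I error. The upper figures, about 12% for a binary outcome and 13.5% for ANCOVA, need stronger assumptions. The documents supply no rates and do not fix the direction.

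Safety removal raises a smaller question. Study labs are drawn only at pretreatment and 6 months, so an enzyme trigger on post-baseline study labs arises when outcomes are due anyway. Only the use of those data is unstated.

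**What to change.** 1. **Data and Safety Monitoring Plan.** For noncompliance, separate stopping capsules from follow-up and keep the return provision unchanged. Suggested text: *Subjects found noncompliant remain in outcome follow-up; the scheduled standard-of-care 6-month scan and labs are obtained and used, subject to consent.*
2. **Safety removal.** Leave the rule clinically as it is. Reconcile it with the analysis text by stating only that 6-month outcome data available from routine care are used where consent allows.
3. **Data Analysis, B.** Add: *The primary analysis includes all randomised subjects in the arm assigned, regardless of compliance, using every available 6-month outcome, with a sensitivity analysis for missing outcomes. A compliers-only analysis, with compliance defined in advance, is supportive. Removals are reported by arm and reason.*

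**Cost.** The change needs a protocol, SAP and IRB amendment. The scan and labs are already standard of care. The consent form (Attachment A) was not available for this review, so permission to use data after removal must be confirmed. Recruitment spans 2019-2021 and this version is dated 04/07/2021, so some early removals may be unrecoverable. Partial recovery still helps. If a fraction f of removed subjects is recovered at random, the arm mean is r·φ(z_p)(1 − f)/(1 − p + fp). For 20% v 40% and r = 0.3 to 0.5, f = 0.5 cuts the bias from 0.09-0.15 to 0.03-0.04 SD.

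The power cost against compliers-only, at the assumed 0.9 SD, is about 5 points (95.0% − 89.6%) or 24 points (91.5% − 67.5%) if 20% or 40% of the probiotic arm gain nothing. On the plan's effect size, 80 subjects hold 80% power down to about 70% compliance.
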